#### Analysis

These interviews will be transcribed and thematically analysed, focusing on content relevant to development of the intervention. The team will use a thematic analysis (Braun et al., 2018) facilitated by NVivo software and a collaborative approach using Saunders (2023). To minimise bias and ensure emerging themes are valid, development of codes and themes will be done collaboratively, led by LB with input from supervisory team and trained LEAP members. With further validity, through a supervisory team member conducting a second coding of 20% of transcripts and the use of reflexive diary by LB and field notes after each interview/ focus group. To ensure transparency, a clear audit trail will be saved on NVivo. Data analysis will be conducted in collaboration with lived experience researchers and the LEAP group, following best practice guidelines to ensure a rigorous and inclusive approach (Jennings et al., 2018; Saunders et al., 2023) .

#### 6.3. WP2 Co-design Workshops

Intervention design will be based on a creative co-design approach through 2 workshops with N= 20 participants for each workshop. Two stakeholder workshops will be organised and facilitated by the research team and Lived Experience Advisory Panel (LEAP) members. The workshop's objective is to produce a prototype of the intervention for testing. A co-design approach has meaningful service user involvement (Slattery et al., 2020) and is advocated for "groups who are often excluded from research" s (Moll et al., 2020; O'Cathain et al., 2019; Slattery et al., 2020b). Using creative methods overcomes challenges like power, language, and time. The creative methods such as mapping, brainstorming, concept posters and storyboards to engage participants and share and develop ideas for innovative solutions (Langley, n.d.; Moll et al., 2020; O'Cathain et al., 2019) Extra support will be given to service user and carer participants to help them attend and participate.

For the co-design workshops, it is critical to include a wide variety of perspectives from diverse stakeholder groups. However, recognising that some interested individuals may not be able to attend due to scheduling conflicts or other barriers, supplementary interviews or small group meetings will be conducted. These additional sessions will aim to gather input from underrepresented stakeholder groups, ensuring their perspectives and ideas are incorporated into the development process.

The supplementary interviews or meetings will cover the same areas as the workshops. For **Workshop 1**, this will involve generating intervention ideas, discussing the findings from WP1, and brainstorming potential solutions. For **Workshop 2**, the focus will shift to refining proposed interventions, addressing implementation challenges, and discussing the feasibility of ideas. These sessions will help ensure the intervention design reflects a broad range of experiences and needs.

### ***Workshop 1 – Idea generation***

The first workshop will involve generating intervention ideas and drafting the logic model. Key findings from WP1 will be shared. Areas covered may include the impacts on service users of the MHA assessment, such as aspects resulting in confusion and perceived unfairness. Current practice will be compared with service user and carer views about what would ideally post MHA. Both service users and staff participants will be encouraged to make suggestions for the intervention. The LEAP will help develop easy-to-understand visual representations of findings data analysis.(Grindell et al., 2020a; Langley, n.d.; O'Cathain et al., 2019) . Intervention ideas will be refined through a series of activities and polls (Grindell et al., 2020a; Langley et al., 2018)

By the end of the workshop, attendees will have voted on the best intervention ideas. the research team will produce a mock-up of one or two top ideas, highlighting key elements and alternative options for Workshop 2 discussion. A storyboard and/or draft resource will represent the ideas, providing a tangible focus for further development (Grindell et al., 2020b)

### ***Workshop 2 – further designing and selecting for prototype***

In Workshop Two the draft logic model with key components will be shared and discussion and agreement on key intervention components. Then the participants will refine the intervention and assess ease of use and practicality. Ideas for the manual for the intervention will then be discussed, as well as implementation challenges. ]. An accompanying draft logic model will also be produced from this workshop.

The research team will further draft the intervention manual incorporating ideas from Workshops. The Template for Intervention Development and Replication (TIDieR) checklist will be used to ensure key ingredients are all specified(Hoffmann et al., 2014).

The outputs from this Work package will be, a prototype intervention including accompanying draft resources and a logic model.

## **7. TRIAL PROCEDURES**

This study involves a novel clinical intervention; however, it is not a full clinical trial. The intervention will be delivered on a small scale to a maximum of six individuals using NHS services, primarily to test feasibility, acceptability, and usability in a real-world setting. The purpose at this stage is not to evaluate clinical efficacy or compare outcomes against a control group, but rather to refine the

intervention and understand its implementation in practice. It does appear to fall under the definition of a clinical trial as outlined by the Medicines for Human Use (Clinical Trials) Regulations 2004 as it involves administration of novel clinical intervention.

As the study has no pre-intervention assessments as not assessing clinical efficacy. The following section will look at procedures for Work Package 3 (WP3), which focuses on testing and refining the intervention

### 7.1.1 Intervention Procedures

The primary outcomes of WP3, are to ensure its acceptability and practicality and to explore participants' experiences with the intervention through qualitative interviews.

In WP3, the research team will iteratively test and refine the prototype intervention. This will begin with **User Testing** (see Section 5.0.2 for Sampling of Clinical Staff and 5.2.2 for Inclusion Criteria) involving staff participants, followed by **Real-World Testing**, which includes both staff and service user participants (see Section 5.0.1 for Sampling and 5.1.1 for Inclusion Criteria) (O'Cathain et al., 2019). This process is designed to ensure the final intervention is acceptable, feasible, and engaging.

Real-world testing often highlights unexpected challenges in implementation (O'Cathain et al., 2019; Joe et al., 2015). Identifying and addressing these issues during the testing phase helps to refine the intervention and resolve problems before moving to more costly and time-intensive feasibility trials. A small sample size is sufficient for this phase, as the goal is to evaluate intervention acceptability and usability rather than generalizability.

The **Instant Data Analysis (IDA)** process will be used to maximize the usefulness of testing sessions (Joe et al., 2015). This approach combines interviews and brainstorming immediately after testing, allowing the team to address issues while they are fresh in participants' minds. Simple changes will be rapidly incorporated into the intervention between testing cycles, while more complex refinements will be reviewed and agreed upon with the research team and the Lived Experience Advisory Panel (LEAP).

#### ***'User testing' cycle***

Staff participants = 6 will test the prototype intervention and accompanying intervention manual in role plays with a person with lived experience of MHA assessment from the LEAP group. This testing will be recorded and observed by a member of research team. They will receive the intervention and any training resource in advance of the testing. An adapted 'thinking aloud' (Joe et al., 2015; O'Cathain et al., 2019) procedure will be used, inviting participants to share thoughts and comments on the intervention as they use it. Minor amendments will be made prior to the next user testing.

### ***“Real-world testing” cycle***

This testing cycle will involve evaluating the prototype intervention with a staff participant and a service user participant. The staff participant will receive the intervention and any training resource in advance of the testing.

Staff participants will identify service users they work with who meet the sampling criteria (Section 5.1.1). If a service user agrees to participate, they will be consented either together with the staff participant or separately. If both parties are agreeable, the testing session may be recorded; this recording is optional.

The follow-up interviews can take place immediately after the intervention or on a later date, depending on what can be arranged. Staff and service user participants will be interviewed separately to ensure free expression of their views. If both parties agree and it is practical, a joint interview may also be conducted. All interviews will be recorded and will focus on engagement, usability, and the value of the intervention, as well as suggestions for improvement.

As part of user testing, minor refinements to the intervention will be made after each testing session, while more complex adjustments will be undertaken in consultation with the research team.

Following the completion of WP3, interview recordings and field notes will be reviewed to refine a logic model, describing the key components of the intervention, contextual factors affecting how it is delivered, its perceived impacts and the mechanisms by which they are achieved. Together with a description of the iterative development of the intervention will be written up as an academic paper.

## **7.2 Discontinuation/withdrawal of participants**

In consenting to participate in the trial phase (WP3), participants are consenting to testing the and interview following. It is a one-off session.

It is always within the remit of the physician responsible for a service user to withdraw the service user from a trial (or certain aspects of the trial) for appropriate medical reasons, adverse events or new information gained about an intervention. A participant may be withdrawn from this WP whenever continued participation is no longer in the participant’s best interests, but the reasons for doing so must be recorded. Reasons for discontinuing may include deterioration in mental health.

The decision to withdraw a participant from treatment will be recorded in the CRF and medical notes/electronic health record system. If a participant explicitly states they do not wish to contribute further data to the trial their decision must be respected and recorded in the CRF and medical notes. Any inclusion of collected data needs to be used in accordance with GDPR and HRA guidance.

## **7.3 Definition of End of Trial**

The expected duration of the trial is 2.5 from recruitment of the first participant.

The end of trial is the date of the last testing session of the last participant in WP3.

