Trial duration per participant:	Maximum of eight weeks for workshop participants if attend both. For other participants the duration will be between consent and arranging the interviews/ or focus groups up to a month.
Key Study milestones	
study submission 4/2025
 
WP1 first Service user and staff recruitment 8/2025
 
WP1 last participant recruitment 4/2026
 
WP1 analysis finished 6/2026
 
WP2 Workshops completed 3/27
 
WP2 prototype intervention developed 6/27
 
WP3 recruitment to testing 7/27
 
WP3 final recruitment 12/27

Estimated total trial duration:	From 8/25 - 9/28
Planned trial sites:	multi-site North London NHS Foundation Trust, Sussex Partnership NHS Foundation Trust, Hampshire & Isle of Wight Healthcare NHS Foundation Trust
Total number of participants planned:	
WP1 Service user = 20, Staff = 20
 
WP2 Workshop one = 20, workshop two= 20
 
WP 3 User testing = 6 staff Real World testing = 6 staff and 6 service user
 
100 Participants

Main inclusion/exclusion criteria:	For WP1 and WP 3 Service users assessed under MHA adults under 65 with capacity Staff either involved in assessment or care afterwards.

	For WP2 wider stakeholders involved in MHA assessments. People with lived experience need to have prior involvement in collaborative projects.
Statistical methodology and analysis:	No Statistical analysis as not a full clinical trial. Thematic and collaborative analysis of data collection in WP 1. The testing of prototype intervention will use Instant Data Analysis for initial refinements for WP 3.
FUNDING & OTHER	
Funding	NIHR Academy [name] [contact] / [name]
Other support	Hampshire and IOW NHS Healthcare Foundation NHS Trust - Employer of [name] and NHS site sponsor
STORAGE of SAMPLES / DATA (if applicable)	
Human tissue samples	Not applicable
Data collected / Storage	Not Applicable
KEY STUDY CONTACTS	
Chief Investigator	[name] (BLE) Professor of Mental Health and Social Inclusion University College London [name] [name] London [name] [contact] [name]
Study Coordinator	[name] (LB) PhD student Division of psychiatry University College London [name] [name] London [name]

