## 12. RECORDING AND REPORTING OF ADVERSE EVENTS

### 12.1 Definitions

Term	Definition
Adverse Event (AE)	Any untoward medical occurrence in a patient or trial participant, which does not necessarily have a causal relationship with the intervention involved.
Serious Adverse Event (SAE).	Any adverse event that: 
 
• results in death,
 
• is life-threatening*,
 
• requires hospitalisation or prolongation of existing hospitalisation**,
 
• results in persistent or significant disability or incapacity, or
 
• consists of a congenital anomaly or birth defect.
 
• Other ‘important medical events’ may also be considered serious if they jeopardise the participant or require an intervention to prevent one of the above consequences
 

\* A life-threatening event, this refers to an event in which the participant was at risk of death at the time of the event; it does not refer to an event which hypothetically might have caused death if it were more severe.

\*\* Hospitalisation is defined as an in-patient admission, regardless of length of stay. Hospitalisation for pre-existing conditions, including elective procedures do not constitute an SAE.

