## 12.2 Assessments of Adverse Events

WP1 and WP2 involve one-off interviews and stakeholder meetings, with no intervention. We do not propose to formally monitor SAEs in these phases of the study.

WP3 involves clinical staff using our novel intervention with six service user participants. It is possible in theory that service users could experience the intervention negatively and this could result in a serious adverse event. We will monitor SAEs in WP3 through feedback from the involved clinical and service user participants at the time of the intervention and in the follow-up interview.

In addition to SAE monitoring, we will also keep a Harms Log, recording any reported negative experiences of the interviews or intervention across all three Work packages. We will report the nature of the harm, which participant was affected, action taken to resolve the harm, and any actions planned to prevent recurrence. This harms log will be reviewed at least monthly by LB and her clinically qualified supervisors SJ and BLE, and by the wider project management group (see 15.2) at scheduled meetings. It will be available for review by the sponsor as requested. For this study, there will only be Adverse Events and Serious Adverse Events for work package 3.

Each adverse event (AEs) will be assessed for severity, causality, seriousness and expectedness as described below.

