#### 12.4 Managing serious adverse events across research sites (if applicable)

SAEs will be reported to the Sponsor until the end of the trial.

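### The end-of-trial date in 7.3, and with it SAE reporting to the Sponsor under 12.4, can fall before the follow-up interview in which 12.2 plans its second SAE check

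*Protocol*

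**What the plan says.** Five parts of the protocol bear on this.

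- Section 7.3 defines the end of trial: "The end of trial is the date of the last testing session of the last participant in WP3".
- Section 12.4 ties safety reporting to that date: "SAEs will be reported to the Sponsor until the end of the trial".
- Section 12.2 states that SAEs in WP3 are monitored through feedback from the staff and service user participants "at the time of the intervention and in the follow-up interview".
- Section 7.1.1, under the real-world testing cycle, sets the timing of the interview: "The follow-up interviews can take place immediately after the intervention or on a later date, depending on what can be arranged". No maximum interval is given.
- Section 7.1.1 also names the WP3 primary outcomes. They include exploring participants' "experiences with the intervention through qualitative interviews", so these interviews are the outcome data.

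Section 7.2, directly before 7.3, points the other way. It says that WP3 participants consent to the testing and the interview after it, and describes this as a single occasion.

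**The concern.** Section 12.2 plans two looks for SAEs, and 7.3 with 12.4 places the cut-off at the first of them for whoever is tested last. If that person's interview is deferred, the second look takes place when the duty to report to the Sponsor has already lapsed. The six service users in real-world testing are the only people who receive the new intervention as patients, and 12.2 itself accepts that a bad experience of it could in theory lead to an SAE. The interview is the only planned contact at which an event after the session would come to light.

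The same date has a second effect. Interviews that supply the WP3 primary outcome could be held after the study has formally ended, and 14.1 counts the 90-day notification to the ethics committee from that end.

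**Working it through.** There is no sample size, error rate or stated figure to reproduce; section 10 says the study has no statistical considerations. The check is one of dates.

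**Notation.** For service user i (i = 1 to 6, from section 4.3):

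- S_i = date of the testing session
- I_i = date of the follow-up interview
- L_i = I_i − S_i, the interview lag. Section 7.1.1 allows L_i = 0 or L_i > 0, with no maximum.
- E = end of trial = the latest S_i. This follows from 7.3, since real-world testing comes after user testing.

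**Condition for the conflict.** The second SAE check falls after the end of trial when I_i > E, that is, when L_i > E − S_i.

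**Last service user.** Here S_i = E, so E − S_i = 0. Any lag above zero puts the interview outside the trial. With L_i = 0 it is inside.

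**The other five.** E − S_i is the time from their own session to the last one. Their interview is outside only if it is deferred by more than that time. This matters mainly for someone tested shortly before the last session. Section 4.3 describes a cycle in which feedback after each test guides refinement, so earlier interviews would usually be done before the next session.

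**Range.** If every interview is held on or before the date of the last session, 0 of 6 are affected. If all were deferred past it, 6 of 6 would be. The protocol does not allow a narrower figure, because it states neither the S_i nor any limit on L_i.

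**Does another reporting rule remove the cut-off?**

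- Section 12.3 asks for SAE forms to reach the Sponsor within 5 working days of awareness. That sets how fast to report. Section 12.4 sets for how long.
- Section 12.3 also sends unexpected, related events to the Health Research Authority within 15 days. It has no end date of its own, but it is a different recipient and a narrower class of event.
- The Harms Log (sections 11 and 12.2) can record later distress, but 12.2 keeps it in addition to SAE monitoring and shows it to the Sponsor on request.
- Section 12.7 reports serious incidents to the Sponsor with no end date. It is a separate route with its own definition.

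These routes reduce the chance that an event is lost. None of them changes the stated end of SAE reporting to the Sponsor.

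**Room in the timetable.** The planned study end is 9/28. Section 7.3 gives an expected duration of 2.5 without a unit. Reading it as years from first recruitment in 8/2025, 8/2025 + 30 months = 2/2028, which is 7 months before 9/2028.

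**The case against.** The best defence is section 7.2. If testing and interview are one occasion, the last testing session in 7.3 includes the interview, and 7.3, 12.2 and 12.4 agree. Section 7.1.1 lends support: Instant Data Analysis places interviews straight after testing. This stands as far as same-day interviews go, and they may well be the norm. It does not settle the matter, because the same section treats the interview as separate and expressly permits a later date.

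Several stronger readings are tempting, but the documents do not support them.

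- *That the gap applies to the last service user in every case.* It applies only when the interview is deferred past the last session.
- *That the number of late interviews can be estimated from a lag of about a month.* The Study Summary says "For other participants the duration will be between consent and arranging the interviews/ or focus groups up to a month". That month runs from consent to arranging the interview, not from session to interview. Likewise "WP3 final recruitment 12/27" is a recruitment milestone and gives no session dates.
- *That a psychiatric readmission after the session is the SAE that would be missed.* Section 12.1 does list an event that "requires hospitalisation or prolongation of existing hospitalisation", but its footnote excludes hospitalisation for pre-existing conditions, which may cover such a readmission. Death, life-threatening events and important medical events remain.
- *That safety data would be thinnest for the final version of the intervention.* The real-world testing text makes refinements after each session, so the last service user does not clearly receive the final version.
- *That the Appendix 1 grid either sets or wrongly omits a follow-up period.* It is unfilled template, with placeholder days and a randomisation row. That is a clerical matter.

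**Conclusion.** Wrong as written; minor severity. The end-of-trial definition does not cover an interview that the protocol relies on both for its second SAE check and for its WP3 primary outcome. The conflict exists whenever the interview of the last service user, or of one tested shortly before, is held after the last session. It does not exist if all interviews are completed by then.

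The size is bounded at six service users and cannot be stated more closely. What lapses is the 12.4 duty to report to the Sponsor. A reader might infer that a late event would go unrecorded, but the other routes may still capture it. The conclusion rests on reading the testing session in 7.3 as distinct from the interview, as the real-world testing text does.

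**What to change.** In 7.3, define the end of trial as the date of the last follow-up interview in WP3, or of the last testing session if that is later. Make clear that this means whichever WP3 interview falls last, so that a deferred interview of an earlier participant is covered too. Section 12.4 then spans both SAE checks in 12.2 without being reworded, and the primary-outcome interviews fall inside the trial. It would help to align 7.2 by saying that the interview may be held on another day.

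The cost is one reworded sentence and a slightly later end-of-trial date, which fits inside the planned 9/28 end. No extra visits or data are needed.

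A fixed SAE follow-up period after each session, with a check through the care-team participant, would also cover the time after a same-day interview. That is an optional design choice for the clinical supervisors, and the correction does not depend on it.
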